**Baseline Assessment.** To describe the sample, all participants will complete the baseline assessment that will include measures of depression, substance use disorders, PTSD, and trait anxiety as they have been found to increase risk for suicide in Veterans,  treatment engagement which is associated with suicide after discharge from psychiatric hospitalization,  insomnia which may be associated with suicide risk in Veterans,  anger is associated with increased suicide risk and may impact the effectiveness of MI based interventions for Veterans,  and previous suicidal behavior which is a robust predictor of suicide.  Although there are no measures of motivation to live, we are also interested in piloting a motivation to live measure as a potential risk factor. We are also adding three measures that assess mechanisms through which MI-SI may work and therefore serve as short-term outcomes. They will be used to describe the sample and may be controlled for in the analyses if there are differences between conditions.

- 1. Depression (9 items): The Physicians Health Questionnaire (PHQ-9)  is a reliable and valid self-report assessment of depressive symptoms that is used by VA. 
- 2. PTSD (17 items): The PTSD Checklist Civilian Version (PCL-C)  $^{58}$  is a reliable and valid self-report assessment of PTSD symptoms  $^{59}$  that is used with Veterans.  $^{60}$

- 3. Anxiety (21 items): The Beck Anxiety Inventory (BAI)  $^{61}$  is a reliable and valid self-report measure of anxiety.
- 4. Alcohol Use Disorders (10 items): Alcohol Use Disorders Identification Test (AUDIT)  $^{62}$  is a self-report measure designed to assess hazardous alcohol use that is reliable and valid in Veterans.  $^{63}$
- 5. Drug Abuse (10 items): A reliable and valid 10-item short-form of the Drug Abuse Screening Test (DAST)  $^{64}$  will be used to assess non-prescription drug abuse, not including alcohol abuse. The DAST has been used with Veterans.  $^{65}$
- 6. Substance Use Frequency past 90 days / Drug of Choice (12 items): The Substance Use Frequency Form (SUFF) is a measure that was developed by [name] to assess substance use frequency and drug of choice. It is based on questions commonly used in the substance abuse literature.  $^{66}$

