- 7. Drug Use Consequences (15 items): The Inventory of Drug Use Consequences (INDUC)  $^{67}$  is the gold-standard self-report assessment of substance-related consequences in the past 90 days. It has been used with Veterans.  $^{68}$
- 8. Insomnia (7 items): The Insomnia Severity Index (ISI) is a widely used, reliable and valid self-report instrument of sleep difficulty. 
- 9. Anger (5 items): The Lifetime History of Aggression Questionnaire (LHAQ) is a brief, valid, and reliable measure of aggression .
- 10. Treatment Engagement (26 items): Treatment engagement will be measured using the Alcohol and Drug Services, Medication, Medical Services, and Psychological Services sections of the Treatment Services Review (TSR-6) which have been shown to be both reliable and valid. 71 The TSR-6 will be used at baseline and the 1, 3 and 6 month follow-ups to inquire about use of these services. The baseline assessment will be used to compare engagement in psychological and alcohol and drug service use between groups to assess whether it needs to be accounted for in the analyses. Engagement in psychological and alcohol and drug services will also be assessed at each follow-up assessment and used as an exploratory outcome. Treatment engagement will be treated as a dichotomous outcome, and will be defined according to the Substance Abuse and Mental Health Services Administration (SAHMSA) Washington's Circle standards, 72 which have been adopted by VA. 73 For residential patients and inpatients, treatment engagement is defined as attending two outpatient visits in the 30-days after discharge. In Veterans with substance use disorders, this measure of treatment engagement has been found to be associated with treatment outcome 74 and hospitalization in those with a suicide attempt history. 75 In Veterans discharged from psychiatric hospitalization, completing two outpatient sessions in at least two of the six months after discharge has also been found to be associated with suicide. 1
- 11. Suicidal Behavior (18 items): The Colombia Suicide Severity Rating Scale (C-SSRS)  will be used to assess history of suicidal behavior at baseline and at follow-up assessment. It has been mandated for use in medication trials by the FDA. 

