Maintaining Blind Outcome Assessments. In-hospital and post-discharge follow-up assessments will be conducted by research assistants who are blind to condition. The blind will be maintained by having research assistants who are not involved in the baseline and treatment phases of the study conduct the assessment by telephone from the CoE. After each outcome assessment, research assistants will be asked if they thought the participant was assigned to the experimental condition (MI-SI plus TAU), control condition (TAU alone), or don't know which condition the participant was assigned to. They will also be asked how they decided the condition to ensure that the blind was indeed broken and the determination was not due to extraneous information such as positive outcome, which would presumably lead a research assistant to guess the MI-SI plus TAU over TAU alone. If blinding was successful, research assistants will not be able to determine assignment at a better than chance rate. 

Randomization. Prior to randomization, participants will be stratified by SSI scores to increase the probability of balanced assignment, which may decrease the probability of a Type 1 error and increase power.  Stratification will be based on a median split using data from pilot study #1. Participants who score below 24 will be in the lower SSI group, and those who score 24 and above will be in the higher SSI group. A blocked randomization procedure using block sizes of 4 and 6 participants will also be used to assure no significant imbalance between the numbers of participants in each condition at any time, and to protect against guessing condition assignment.  Randomization will occur prior to the start of the trial and the results will be recorded in sealed envelopes. After the baseline assessment, the researcher will choose the next envelope (within the strata and block) to determine the participant's assignment. The researcher will then inform the study therapist that a participant has been randomized to receive MI-SI.

**Treatment Conditions.** Participants will be randomized to MI-SI plus TAU or TAU alone.

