### **Analytical Plan**

**Data Preparation.** All data will be screened for missing data, outliers, non-normality, non-linearity, and non-homoscedasticity. A combination of statistics and graphic representations will be used to complete these screens. Specifically, missing values analyses, descriptive analyses, frequencies, scatter plots and histograms will be used. The assumptions underlying the proposed statistical analyses will also be tested, which may lead to data transformations or the use of more appropriate statistics. Additionally, imbalances in important covariates between randomized groups will be tested at baseline, which may lead to the identification of covariates to be included in the analyses. Findings will be used to fine-tune the analytical plan if statistical assumptions are unmet or model fit is poor. All analyses will be based on an intent-to-treat approach, analyzed as randomized, include all available data, use multiple imputation for missing data if appropriate, and use one-tailed tests with p < .05 as the cutoff for statistical significance. The study is not powered to test exploratory hypotheses, and we therefore do not

expect to detect significant differences between groups. If the analyses are reported as part of the primary RCT, we will use a p-value of .01 to define statistical significance.

**Aim 2:** To evaluate whether MI-SI plus TAU results in significant reductions in suicidal ideation (SI) and increases in treatment engagement when compared to TAU alone.

Primary Hypothesis: Participants who receive MI-SI plus TAU will report greater reductions in SI over follow-up than participants who receive TAU alone.

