Exploratory Hypothesis 2: Treatment engagement over follow-up will partially mediate the impact of MI-SI on SI.

Exploratory Analysis 2: Analyses will examine treatment engagement as a mediator of the impact of MI-SI plus TAU on SI. Treatment engagement is expected to partially mediate the relationship between randomization to the MI-SI group and SI over follow-up, such that the relationship is smaller but the effect size is still significant. Structural equation modeling (SEM) will be used to examine this potential mediation relationship. SEM is a method for creating latent

variables and identifying and describing causal relationships between the latent variables. We decided to use SEM because it simultaneously tests independent and conjoint relationships and uses latent variables, which minimizes measurement error. The model will consist of both latent and observed variables. Latent variables will be used for variables such as SI (via the SSI) to fit the data for this population. Observed variables will be used for variables such as randomization to MI-SI and treatment engagement (via the TSR). Because these analyses will be underpowered, this exploration will be based on effect sizes rather than statistical significance. Furthermore, we will also conduct more basic mediation regression models as secondary analyses.

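### Exploratory Analysis 2 prespecifies no baseline confounder of the engagement-to-SI path, and choosing covariates by arm imbalance would rarely supply one

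*Combined protocol and SAP*

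**What the plan says.** The Analytical Plan, Exploratory Analysis 2, proposes a structural equation model with SI as a latent variable. On the measured side it says "Observed variables will be used for variables such as randomization to MI-SI and treatment engagement (via the TSR"). It adds that "we will also conduct more basic mediation regression models as secondary analyses". Neither model is given a baseline covariate. No assumption about confounding of engagement and SI is stated, and no sensitivity analysis for it is planned.

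Rules for covariates appear elsewhere, and all turn on a difference between arms:

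- Baseline Assessment, Treatment Engagement item: the baseline TSR-6 has this stated purpose: "compare engagement in psychological and alcohol and drug service use between groups to assess whether it needs to be accounted for in the analyses".
- Baseline Assessment, introduction: the baseline measures "may be controlled for in the analyses if there are differences between conditions".
- Analytical Plan, Data Preparation: "imbalances in important covariates between randomized groups will be tested at baseline, which may lead to the identification of covariates to be included".
- Treatment Conditions, TAU: suicide-related usual care is handled by the same kind of rule.

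Two further facts matter. Under Randomization, "participants will be stratified by SSI scores to increase the probability of balanced assignment", with the cut at 24. And the mediator is binary: "Treatment engagement will be treated as a dichotomous outcome", based on outpatient visits after discharge.

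**The concern.** Randomisation makes the arms comparable. It therefore protects the total effect of MI-SI on SI and the arm-to-engagement path. It does nothing for the engagement-to-SI path, since patients who attend visits after discharge select themselves or are steered into care. A baseline characteristic can be perfectly balanced between arms and still differ between those who engage and those who do not. If it also predicts later SI, it confounds that path.

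A test of arm balance is thus the wrong filter for this analysis, and it works worst for the most obvious confounder, because stratification holds baseline SSI close to balance. Judging mediation by effect size instead of significance does not help, because the effect size is what is biased. The plan presents SEM as a way of describing causal relationships, so the result is likely to be read causally and may guide later work on mechanisms.

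**Working it through.** **The plan's own figures.** There is no figure for the mediation analysis. The Power Analysis supplies two inputs used below (SD 8.4; baseline to follow-up correlation .50), so I checked that its results follow from them. For the change method, the variance factor is (1 + 2 × .70)/3 + 1 − 2 × .50 = 0.80 and the effective SD is 8.4 × √0.80 = 7.513. With 45 per arm, one-sided power for 5, 4 and 3 points is .935, .811 and .598 (stated .94, .81, .60). Two-sided power is .884, .714 and .474 (stated .88, .71, .47). All six reproduce. They concern the arm comparison only.

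**Does the arm-difference rule pick up the confounder?** Simulation with 90 participants, arm stratified at the median of baseline severity, binary engagement, a true engagement effect of zero on SI, and 3,000 runs. The severity-SI correlation is .50, as stated. Assumed: the log-odds of engagement per SD of severity or prior service use, a standardised effect of prior use on SI of ±0.2, and p < .05 as the threshold for imbalance. Mean engagement coefficient in SSI points:

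| Scenario | No covariates | Arm-difference rule | Always adjusted |
|---|---|---|---|
| Severity, log-odds ±0.5 | ±2.00 | ±2.00 | 0.00 |
| Severity, log-odds ±0.25 | about ±1.0 | about ±1.0 | about 0 |
| Severity ±0.5 plus prior use 0.5 to 1.0 (absolute value) | 0.3 to 3.1 | 0.4 to 3.0 | about 0 |

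The rule selected baseline severity in about 0.1% of trials and prior service use in about 5%, which is chance. With simple randomisation, severity was selected in about 6%. The bias does not shrink with sample size: one scenario gave 2.65 points at both n = 90 and n = 20,000.

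**Size over a range of correlations.** Let severity correlate r₁ with a normal propensity to engage and r₂ with follow-up SSI, and let a proportion p engage. With no true engagement effect, the unadjusted difference between engaged and not engaged is

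8.4 × r₁ × r₂ × φ(z)/[p(1 − p)], where Φ(z) = p.

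The last factor is .3989/.25 = 1.596 at p = .50 and .3477/.21 = 1.656 at p = .70, so p matters little.

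- r₁ = r₂ = .3: 8.4 × .09 = 0.756, giving 1.21 to 1.25 points.
- r₁ = r₂ = .4: 8.4 × .16 = 1.344, giving 2.14 to 2.23 points.
- r₁ = r₂ = .5: 8.4 × .25 = 2.10, giving 3.35 to 3.48 points.

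Simulation agrees, with about 1.2 to 1.3, 2.1 to 2.2 and 3.4 to 3.5 points, and about zero once severity is in the model.

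**Sign.** Suppose severity is baseline SSI itself, with r₂ = .50, equal SDs at baseline and follow-up, and p = .64 (assumed; factor .3741/.2304 = 1.624). On follow-up level, r₁ = .3, .4 and .5 give 8.4 × .50 × r₁ × 1.624 = +2.0, +2.7 and +3.4. On change (follow-up minus baseline), the slope on severity is .50 − 1 = −.50, so the bias has the same size and the opposite sign. A negative r₁ reverses both.

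**Indirect effect.** This is a × b, where a is the arm difference in the proportion engaged. The documents give no a; I assume .10 to .30. A bias of 1.2 in b becomes 1.2 × .10 = 0.12 to 1.2 × .30 = 0.36 points. A bias of 3.5 becomes 0.35 to 1.05 points.

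**The case against.** Several counter-arguments have weight.

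- **The variable list is open.** The latent and measured variables are both introduced as examples, so baseline SSI might enter the model. The secondary regressions carry no covariate rule of their own; that the general rule applies to them is an inference. This stands. The supportable statement is that no confounder is prespecified, not that the model contains only arm, engagement and SI.
- **Direction.** A reader might infer that sicker patients get more visits, so that engagement will look useless or harmful and a real mediated benefit will be hidden. The documents do not support that. Treatment Conditions describes staff who help suicidal patients move into outpatient care, which suggests more engagement with severity. Background and Significance argues that Veterans in whom the wish to die dominates may refuse treatment, which suggests less. Exploratory Analysis 2 also does not say whether SI is modelled as level or change, and that alone reverses the sign.
- **Scale.** It is tempting to set a bias of up to 3.5 points beside the 4 to 5 point differences in the Power Analysis. Those are arm effects. The mediated quantity is a × b, and its bias is several times smaller.
- **Status.** The analysis is exploratory, declared underpowered, and separate from the primary result. That limits the severity. It does not remove the bias, which would persist in a larger sample.

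**Conclusion.** The point holds, as a minor one. The plan names no baseline confounder of engagement and SI, and its only stated route for covariates is a difference between arms, which leaves the bias on this path essentially unchanged. Baseline severity, depression and prior service use can bias the engagement coefficient by about 1.2 to 3.5 SSI points in absolute value. The indirect effect is biased by that amount multiplied by the arm difference in engagement.

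The range rests on assumed correlations of .3 to .5; only the .50 correlation between baseline and follow-up SSI is in the documents. Weaker associations give less bias, and confounders acting in opposite directions can partly cancel. In the first pilot all 13 participants had received treatment in the prior year, so prior use would act through its amount. The direction cannot be settled from the documents. The primary analysis is not affected.

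**What to change.** In Exploratory Analysis 2, for both the SEM and the secondary mediation regressions, always include baseline SSI, baseline TSR-6 engagement and baseline PHQ-9 in the engagement equation and in the SI equation, regardless of arm balance. Because engagement counts alcohol and drug services, add a baseline substance use measure such as AUDIT or DAST-10. State whether SI is modelled as level or change. Report the indirect effect as conditional on no other confounding; baseline adjustment cannot deal with factors that arise after randomisation.

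The cost is a few sentences. Every measure is already collected at baseline. The downside is four more coefficients per equation in a small model. If 64% of 90 participants engage (assumed), about 32 do not (90 × .36 = 32.4). Arm plus four covariates then leaves about 6 non-engagers per coefficient in the engagement equation, so that equation should be kept to these terms.

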Power Analysis: Recruitment will provide data on 112 participants. Assuming a retention rate of 80%, data on 90 participants will be available at the 6 month follow-up. To estimate the statistical power afforded by 90 participants for the severity of SSI, power analyses were conducted using STATA 11 101 "sampsi2" package, which uses calculations based on Frison and Pocock model. 102 Specifying method of analysis (change), number of baseline assessments (1), number of post assessments (3), correlation between baseline and follow-up scores (r = .50), correlation between follow-up scores (r = .70), and standard deviation (sd = 8.4) for the outcome variable using Frison and Pocock's recommendations and our pilot data. we would have .94 power to identify a 5-point difference in mean SSI scores between treatment arms, .81 power to identify a 4-point difference, and .60 power to identify a 3-point difference. The study would therefore be adequately powered to find an effect size of .5 for the primary outcome. If there is concern that the experimental intervention caused harm and the trial is not stopped, we will conduct two-sided analyses instead of the one-sided analyses we proposed. Power analyses suggest we will have .88 power to identify a 5-point difference, .71 power for a 4-point difference, and .47 power for a 3-point difference with the proposed 90 participants (45 in each group), indicating that the trial will still be fairly well powered.

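### Exploratory Analysis 2 plans no interval for the indirect effect, and the only pattern it describes for partial mediation often appears when there is no mediation

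*Combined protocol and SAP*

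**What the plan says.** Under Exploratory Analysis 2 in the Analytical Plan, engagement is expected to mediate part of the effect of randomization to MI-SI on SI, "such that the relationship is smaller but the effect size is still significant". On method, "Structural equation modeling (SEM) will be used to examine this potential mediation relationship", with SI as a latent variable and arm and engagement as observed variables. Citing low power, the paragraph then says that "this exploration will be based on effect sizes rather than statistical significance", and it ends with "we will also conduct more basic mediation regression models as secondary analyses".

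The paragraph does not name the indirect effect, an interval, a bootstrap, or an amount of shrinkage that would count as mediation. The 95% confidence intervals mentioned in the Analytical Plan belong to the odds ratios of Exploratory Analysis 1.

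The general rules under Data Preparation are to "use one-tailed tests with p < .05 as the cutoff for statistical significance". For exploratory analyses the rule is: "If the analyses are reported as part of the primary RCT, we will use a p-value of .01 to define statistical significance". The same paragraph says the study is not powered for the exploratory hypotheses.

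**The concern.** There are two difficulties. First, the paragraph describes the expected result partly by significance and then sets significance aside, so a reader cannot tell how Exploratory Hypothesis 2 will be assessed. Second, neither reading gives a usable basis. Adding a variable that mediates nothing still moves the arm coefficient up or down by chance. If significance is dropped, what is left is whether the adjusted effect is smaller, which is close to a coin toss. If significance is kept, the pattern mostly reflects whether the total effect was significant in the first place.

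An effect size from about 90 people, given without an interval, does not show whether the data are compatible with no mediation. What is at stake is a statement that engagement carries part of the benefit, made in a report of a positive primary result when chance alone would often produce the same picture.

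**Working it through.** **Inputs from the documents.** The Power Analysis paragraph gives 90 participants (45 per arm), SSI SD 8.4, baseline to follow-up correlation 0.50, correlation among follow-ups 0.70, three follow-ups and analysis of change. The engagement measure is dichotomous (Baseline Assessment, item on treatment engagement).

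**Assumptions.** The documents give no engagement rate on the trial's definition. I use 64% in both arms (borrowed from the first pilot, 7 of 11, where the definition was four or more sessions), or 50% v 75% where MI-SI affects engagement. Where engagement affects SI, the effect is set at 4 points. Linear regression on mean change stands in for the SEM. It is close to the simpler regression models that the plan also names.

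**Step 1: reproduce the plan's power.**
- Variance factor for change = (1 + 2 × 0.70)/3 + 1 − 2 × 0.50 = 0.80.
- SD = 8.4 × √0.80 = 7.51. SE of the arm difference = 7.513 × √(2/45) = 1.584.
- One-sided power = Φ(δ/1.584 − 1.645): .935, .811 and .598 for 5, 4 and 3 points (plan: .94, .81, .60).
- Two-sided: .884, .714 and .474 (plan: .88, .71, .47).

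The plan's figures are reproduced, so the simulations use the same SD.

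**Step 2: why shrinkage is nearly a coin toss.** In linear regression, total effect − direct effect = a × b, where a is the estimated effect of arm on engagement and b the estimated effect of engagement on SI given arm. With no mediation at least one true path is zero, so its estimate is positive or negative about equally often. In the simulations the adjusted effect was smaller in 46 to 50% of no-mediation trials at almost every effect size.

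**Step 3: rate of the pattern with no mediation.** There were 20,000 trials per setting and three settings: neither path present; arm affects engagement only; engagement affects SI only. The pattern is an adjusted arm effect that is smaller and still significant at one-sided .05. The last column is column 3 divided by column 2 within each setting; for example, at 3 points .2356/.5924 = 40% and .2668/.5664 = 47%.

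| True total effect | Total effect significant | Pattern, all trials | Pattern, given a significant total |
|---|---|---|---|
| 0 points | 5% | 1.5–2.2% | – |
| 3 points | 57–59% | 24–27% | 40–47% |
| 4 points | 79–81% | 36% | 44–46% |
| 5 points | 92–93% | 42–44% | 45–47% |

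A repeat run with the same inputs gave 40 to 48% for the last column. With neither path present, the all-trials rates at 3, 4 and 5 points are 13%, 24% and 35% at one-sided .01, and 20%, 31% and 39% at two-sided .05. With all 112 participants at one-sided .05 they are 30%, 40% and 45%.

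**Step 4: the same question with an interval.** A percentile bootstrap 95% interval for a × b (600 trials, 600 resamples each, totals of 4 and 5 points) excluded zero in 0 to 3.7% of no-mediation trials. The simulation error on the largest value is √(0.037 × 0.963/600), about 0.8 percentage points.

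**Step 5: one setting with true mediation.** Take engagement of 50% v 75%, an engagement effect of 4 points and a direct effect of 4. The indirect effect is 0.25 × 4 = 1 point and the total is 5.
- The pattern appeared in 76% of trials, against 42 to 44% with the same total and no mediation: a ratio of about 0.76/0.44 = 1.7.
- The interval excluded zero in 43%, against at most 3.7%: a ratio of about 0.43/0.037 = 12.

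**The case against.** The strongest reply is that the smaller-but-significant wording states what the investigators expect, not how they will decide. That is right. No sentence says Hypothesis 2 will be declared supported whenever the pattern appears, and a reader who infers such a rule goes beyond the text. The point that remains is narrower: the paragraph offers no other criterion.

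A reader might also infer that the pattern arises in nearly half of all trials without mediation. The calculations do not support that as a general statement. It needs a significant total effect, or a true effect near 5 points. With no treatment effect the rate is about 2%, and at the .01 threshold it is 13 to 35%.

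The rates also count trivial shrinkage. Among trials with a significant total effect of 3 to 5 points, shrinkage of at least 10% occurred in only 1 to 13%. At least 20% occurred in 0 to 2% in a run with a total effect of 0.6 SD. A sensible effect-size judgement would therefore be misled less often. But these cut-offs are mine, and the plan sets none.

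It is tempting to add that the mediation result will steer later research on mechanism. The documents do not say so. The Specific Aims mention future mechanism studies only in general terms, and the Background summary names in-session talk as the hypothesized mechanism.

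Finally, the analysis is openly exploratory and underpowered, and requiring an interval to exclude zero would bring back the significance test that the plan set aside. The first part limits how serious this is. The second is a fair objection to a pass/fail rule, but not to reporting an interval.

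**Conclusion.** The concern holds in a limited form. The two statements in Exploratory Analysis 2 conflict, no uncertainty is planned for the indirect effect, and the pattern described separates mediation from chance poorly. The conditional rate of about 40 to 48% is the relevant one when mediation is discussed after a positive primary result.

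The rates depend on the assumed engagement figures, on linear regression in place of the latent-variable SEM, and on counting any shrinkage. The absence of a planned interval and the conflict in wording depend on none of these. Since the analysis is exploratory and the primary comparison is unaffected, this is a minor improvement, not a flaw in the trial.

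**What to change.** In Exploratory Analysis 2, replace the smaller-but-significant description with wording such as: *The mediation result is the indirect effect of MI-SI on SI through treatment engagement, reported with a bootstrap 95% interval from the SEM and from the regression models. Shrinkage or continued significance of the direct effect will not be used to judge mediation. An interval that includes zero will be reported as inconclusive, not as evidence of no mediation.*

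The last sentence is needed because power is low: about 43% in the one true-mediation setting examined. The cost is a short wording change and a bootstrap run on data already being collected. The downside is that support for Exploratory Hypothesis 2 will be claimed less often.
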